9.7.9 Additional Respiratory Tract Symptoms Questionnaire

Additional respiratory tract symptoms will be collected and administered in the same format as the CARIFS. This questionnaire will comprise the record of the incidence, duration, and severity of the individual symptoms. Each item is answered on a 4-point scale (no problem = 0, minor problem = 1, moderate problem = 2, major problem = 3), with a higher score denoting a more severe illness. Participants will complete the questionnaire daily throughout run-in and the study period as part of their study diary.

Additional Symptom data to be collected for the following respiratory symptoms: yellow mucus, bloody mucus, crystalline mucus, itchy nose, itchy throat, red eyes, hoarseness, and sneezing (Section 16.3).

Incidence, duration, and severity of symptoms will be defined as the following:

- Incidence of a symptom will be defined as the first day with a score of greater than 0
- Duration of a symptom will be defined as the length of time from the onset of an incidence (defined above) until the last day the symptom is reported followed by a day with a score of 0
- Severity of a symptom will be calculated using two methods: 1) The mean of the specific symptom scores during the investigational period, and 2) the area under the curve (AUC) of individual symptom scores during the investigational period.

9.8 Compliance

Compliance will be assessed at end of study by counting the returned unused study product at each visit. Compliance is calculated by determining the number of dosage units taken divided by the number of dosage units expected to have been taken multiplied by 100.

$$\frac{\textit{number of dosage units taken}}{\textit{number of dosage units expected to have been taken}} \times 100\%$$

In the event of discrepancy between the information in the study diary and the amount of study product returned, use will be based on the product returned unless an adequate explanation for the discrepancy has been provided. Participants found to have a compliance of <80% or >120% will be counseled.

During remote visits, compliance will be reviewed by asking participants and/or caregivers to count unused investigation product while also reviewing study diaries for possible discrepancies. Participants will be counseled during remote visits regarding study requirements as necessary.

9.9 Laboratory Analyses

Blood, saliva, and stool samples will be collected from the participants at baseline (Visit 2, Day 0) and at the end of study visit (Visit 5, Day 84± 2 days)or Early Termination Visit as indicated in the Schedule of Assessments.

Protection of participant confidentiality will extend to all data generated from the assaying of these samples. These samples will be alphanumerically coded, and the persons performing the analysis will not be aware of the participant's identity or the product they received.

The total blood volume collection for the laboratory assessments listed above will be approximately 60 mL, over the period from screening to end of study (approximately 131 days). At any study visit, blood loss per volunteer is not expected to exceed 30 mL. Additional blood samples may be collected during the course of the study in order to perform or repeat laboratory tests outlined in the Schedule of Assessments if needed.

External laboratories will be used in this study to measure blood parameters.

Urine pregnancy test will be performed at the clinic site during the screening visit (V1), baseline visit (V2), and the end of study visit (V5) or Early termination visit for participants of child bearing potential.

9.10 Termination of the Study

In the case of premature termination of the Study, participating investigators/participants, and the Institutional Review Board (IRB) must be promptly informed of the termination. In the event of early termination, as many assessments will be completed as agreed upon by the participant.

9.11 Protocol Amendments

If amendments to the study protocol are required after approval such changes will be captured in writing, the reasons for the change documented, and signed and dated by the Sponsor. Any such amendments may be subject to IRB and Health Canada review/approval prior to implementation. Exception: if it becomes necessary to alter the protocol to eliminate an immediate hazard to participants, an amendment may be implemented prior to IRB approval. In this circumstance, the Qualified Investigator must notify IRB and Health Canada in writing within five (5) working days of the implementation.

10 SAFETY INSTRUCTIONS AND GUIDANCE

10.1 Adverse Events

10.1.1 Adverse Events

An adverse event (AE) is any untoward medical occurrence in a clinical investigation participant who has been administered an investigational product and does not necessarily present as having a causal relationship with this investigational product. The absence or presence of the causal relationship will be determined by the QI. An AE can be any unfavorable and unintended sign, symptom, or disease temporally associated with the use of a product, and whether or not it is considered related to that product. Pre-existing conditions that worsen during a study are to be reported as AEs and will be reviewed by the QI to provide classification.

During the study, participants should record any adverse effects in their diary. At each visit the participant will be asked, by the investigator: "Have you experienced any changes in your health since your last visit to the clinic?". Any AEs will be documented in the study record and will be classified according to the description, duration, intensity, frequency, and outcome by the medical team. The QI will assess all AEs and decide causality.

Intensity of AEs will be graded on a three-point scale (mild, moderate, severe) and reported in detail in the study record:

Mild: Awareness of event but easily tolerated

Moderate: Discomfort enough to cause some interference with usual activity

Severe: Inability to carry out usual activity

The causality relationship of investigational product to the AE will be assessed by the QI as either:

Most probable: There is a reasonable relationship between the investigational product and AEs.

The event responds to withdrawal of investigational product (dechallenge) and

recurs with rechallenge when clinically feasible.

Probable: There is a reasonable relationship between the investigational product and AEs.

The event responds to dechallenge.

Possible: There is a reasonable relationship between the investigational product and AEs.

Dechallenge information is lacking or unclear.

Unlikely: There is a temporal relationship to the investigational product administration but

there is no reasonable causal relationship between the investigational product and

the AEs.

Not related: There is no temporal relationship to investigational product administration or there

is a reasonable causal relationship between non-investigational product, concurrent

disease, or circumstance and the AEs.

10.1.2 Serious Adverse Event

A SAE is any experience that suggests a significant hazard, contraindication, side effect or precaution. It is any AE that results in any of the following outcomes:

- Death
- A life-threatening AE
- Inpatient hospitalization for 24 hours or prolongation of existing hospitalization
- A persistent or significant disability of incapacity
- A congenital anomaly/birth defect in the offspring of a participant who received the study investigational product

Important medical events that may not be immediately life-threatening or result in death or hospitalization but may jeopardize the participant or may require intervention to prevent one of the outcomes listed above. Examples of such events are intensive treatment in an emergency room or at home for allergic bronchospasm; blood dyscrasias or convulsions that do not result in hospitalization; or the development of drug dependency or drug abuse.

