10.1.3 Unexpected Adverse Reaction

An unexpected adverse reaction is an event that occurs the nature and severity of which is not consistent with the applicable product information (e.g., Investigator's Brochure for an unapproved investigational product or package insert/summary of product characteristics for an approved product).

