10.3 Reporting of SAEs and Unexpected Adverse Reactions

The QI will be responsible for classification of an AE as an SAE within 24 hours of notification. Causality should be signed off by the QI prior to reporting to ethics and regulatory bodies. Notification of any SAEs must be made in writing to the study Sponsor. The IRB will be notified of all product related SAEs and unexpected adverse reactions. All blinded SAE's or unblinded-participant-on-active product SAE's will be reported to the Natural and Non-prescription Health Products Directorate (NNHPD) Clinical Trial Unit in an expedited manner.

KGK Science Inc. must notify the NNHPD of all blinded or unblinded-participant-on-active product SAEs and reactions as follows:

If it is neither fatal or life threatening, within 15 calendar days after the day on which the Sponsor becomes aware of the information; and

If it is fatal or life threatening, must be reported as soon as possible, but not later than seven (7) days after the day on which the Sponsor becomes aware of the information.

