13.3 Potential Risks and Procedures to Minimize Risk

All potential risks are disclosed to study participants prior to their participation. Potential side-effects of taking the study product may include:

- Abdominal discomfort (such as pain, nausea, changes in bowel habits)
- Dislike of taste
- Worsening of URTI or GITI symptoms

OTC medications for fever, cough etc. can be taken and use is to be documented as part of concomitant medications (see Section 9.7.6). If symptoms persist or worsen, participants will be instructed to contact their heathcare practitioner to ensure that any standard of care treatment can be provided.

Other potential risks associated with this study include venipuncture and the associated risks. Risks associated with venipuncture include pain, bruising, and infection at the site. Alcohol swabs and proper venipuncture procedure will be followed to minimize the risk of infection.

Potential Risks From E-Consent

Participants may receive a link via email/text message to download a PDF copy of the signed consent form. There may be risks of loss of privacy and confidentiality if the PDF copy of this consent form is viewed and/or stored on a personal electronic device (PED), especially if that PED is shared with other users or is lost, hacked, or subject to a search warrant or subpoena. Also, the PDF copy of the consent may not be able to be permanently removed from a PED.

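### Section 10.1.2 lists a new admission as an SAE outcome only at 24 hours, and its important-medical-event text does not reliably cover shorter stays; the wording of 10.1.3 leaves a smaller reporting gap

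*Protocol*

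**What the plan says.** Protocol section 10.1.2 defines an SAE as an AE with one of five listed outcomes. The third is "Inpatient hospitalization for 24 hours or prolongation of existing hospitalization". Below the list stands a separate passage that begins "Important medical events that may not be immediately life-threatening or result in death or hospitalization but may jeopardize the participant or may require intervention". It goes on to refer to preventing the listed outcomes, but it has no main verb and does not state that these events are SAEs. Its examples include "intensive treatment in an emergency room or at home for allergic bronchospasm", and blood dyscrasias or convulsions where the child is not hospitalized.

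Section 10.1.3 calls a reaction unexpected when it is an event "the nature and severity of which is not consistent with the applicable product information". The Investigator's Brochure is given as one example of such product information.

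Section 10.3 attaches the reporting duties to these terms:

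- The Qualified Investigator classifies an AE as an SAE within 24 hours of notification.
- SAEs are notified to the sponsor in writing.
- "The IRB will be notified of all product related SAEs and unexpected adverse reactions".
- SAEs that are blinded, or unblinded on active product, go to the NNHPD on an expedited timetable. One sentence there extends this to SAEs and reactions.

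Section 10.1.1 grades intensity separately, with the top grade defined as "Severe: Inability to carry out usual activity". Section 13.3 lists potential side effects with no limit on severity. They include abdominal discomfort and "Worsening of URTI or GITI symptoms".

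**The concern.** The definitions in 10.1.2 and 10.1.3 decide which events leave the site as individual reports and which appear only in the AE tables at the end. In healthy children aged 6 to 12, an admission is an event that the sponsor, the IRB and the regulator would want to hear about promptly. A duration threshold on admission, with only an incomplete and judgement-based clause behind it, means that such an event may not be reported as an SAE.

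The same term is used elsewhere. Section 7.4 allows withdrawal at the investigator's discretion after an SAE, and section 8.8 refers to an SAE when describing emergency unblinding.

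The wording of 10.1.3 raises a lesser worry of the same kind: a reaction of a known type but of surprising severity may not count as unexpected.

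**Working it through.** No arithmetic applies. The protocol gives no admission or reaction rates, and the point depends on no sample-size or test input. The check is to follow specific cases through sections 10.1.1, 10.1.2, 10.1.3 and 10.3. The 18-hour stay is an illustration; any stay under 24 hours would serve.

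**Case 1: a convulsion treated without admission.** It meets none of the five outcomes in itself, but it is a named example in the important-medical-event text. If that text is taken to define SAEs, the event is an SAE and the notices in 10.3 follow.

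**Case 2: a convulsion with an 18-hour admission.**

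1. Hospitalization outcome: not met, because the stay is under 24 hours and no existing stay was prolonged.
2. Other outcomes (death, threat to life, disability, birth defect): not met unless the facts of the case say so.
3. Named convulsion example: not met, because it is limited to convulsions without hospitalization.
4. General important-medical-event wording: available by judgement, but it is framed around events that may not lead to hospitalization, and it never says they are SAEs.
5. Result under 10.3: unless step 2 or step 4 brings it in, it is not an SAE. The written notice to the sponsor, the IRB notice of product-related SAEs and the expedited NNHPD report of SAEs are not triggered. If the event is product-related and also meets 10.1.3, the IRB still hears of it as an unexpected adverse reaction.

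**Case 3: a product-related reaction of a listed kind, graded severe, with none of the SAE outcomes.**

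1. Severe in 10.1.1 is an intensity grade and is not one of the outcomes in 10.1.2, so the event is not an SAE on that ground.
2. Suppose that the product information lists this kind of effect, but only in milder form. Nature is then consistent and severity is not.
3. If 10.1.3 requires both to be inconsistent, the reaction is not unexpected, and the IRB notice in 10.3 is not triggered.
4. If nature and severity are read as one joint profile, a departure in severity suffices, and the IRB is notified.

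**Case 4: as case 3, but the reaction meets an SAE outcome.** Section 10.3 sends product-related SAEs to the IRB, and blinded or active-product SAEs to the NNHPD, with no condition on expectedness. The wording of 10.1.3 makes no difference here.

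Case 2 is the main gap. Case 3 is the limit of the second gap: non-serious reactions, of a listed kind, with unexpected severity.

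**The case against.** The best reply on 10.1.2 is that the section already has a backstop. The important-medical-event passage stands under the SAE heading, its purpose is plain despite the grammar, and an investigator would use it for any grave short admission. The section also opens with broad language about significant hazard. Much of this stands: a short admission is not barred from being an SAE. But the opening language is followed at once by a definition through listed outcomes, and the backstop makes classification depend on judgement where a 24-hour stay is classified automatically. The gap is narrower than the bullet alone suggests, but it is not closed.

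A reader might infer that the definition runs backwards, so that a child treated without admission outranks one who is admitted. The documents do not support that. The emergency-room example concerns intensive treatment for allergic bronchospasm, and it qualifies through the same kind of judgement that could capture a short admission of equal gravity. The difference shown is between automatic and judged classification.

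On 10.1.3, three objections stand:

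- The phrase can be read as one joint profile, so the narrow reading is permitted but not compelled.
- Expectedness is measured against product information that is not at hand. Section 13.3 discloses potential risks and is not named as the reference. It does not follow that the symptom groups in 13.3 are excluded from being unexpected at any severity.
- The NNHPD sentence on SAEs and reactions is not limited to unexpected reactions, so a missed regulator notice is not shown for case 3.

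Nor are these events lost. Under 10.1.1, 10.2 and 11.3.2 all AEs are graded, assessed for causality, followed up and reported. What can be missed is the individual notice.

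**Conclusion.** The point holds as a defect of wording with a practical consequence. The main part is 10.1.2: a new admission under 24 hours meets no hospitalization criterion, and the text that might catch it is unfinished, outside the list and dependent on judgement. Such an event can miss the SAE notices in 10.3. The secondary part is 10.1.3, an ambiguity that touches only non-serious reactions of a listed kind with unexpected severity, and chiefly the IRB notice. It rests on the assumption that the product information lists effects like those in 13.3.

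The size cannot be given as a number. The planned sample is 100 children followed for 84 days, and the protocol offers no basis for an admission rate or for the share of short stays. The count could be zero. A reader might be tempted to state a percentage of admissions lost; nothing in the protocol supports one. The case for changing the text is that individual safety notices should not turn on a duration threshold or on one conjunction. It is not that many events are expected.

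The judgement is also internal to the protocol. It commits to ICH-GCP but does not reproduce those definitions, so the test used here is whether 10.1.2 and 10.1.3 serve the protocol's own reporting rules in 10.3.

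**What to change.** Three wording changes in one amendment:

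1. In 10.1.2, strike the 24-hour qualifier, so that the outcome is inpatient hospitalization, or prolongation of an existing one, with no minimum stay.
2. In 10.1.2, complete the important-medical-event sentence and move it into the list as an explicit SAE criterion, so that the named examples are SAEs by definition.
3. In 10.1.3, replace *nature and severity* with *nature or severity*.

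While 10.3 is open, state whether *reactions* in the NNHPD sentence means unexpected adverse reactions.

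The cost is the amendment itself, with IRB and Health Canada review as required by sections 9.11 and 11.5, and at most a few additional reports. No endpoint, analysis, sample size or rule of clinical care changes.

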10.1.3 Unexpected Adverse Reaction

An unexpected adverse reaction is an event that occurs the nature and severity of which is not consistent with the applicable product information (e.g., Investigator's Brochure for an unapproved investigational product or package insert/summary of product characteristics for an approved product).

10.2 Treatment and Follow-up of AEs

All AEs, especially those for which the relationship to the investigational product is suspected, should be followed up, by the investigational team until they have returned to baseline status or stabilized in the participant. Such events and the follow-up need to be recorded to bring closure to the event, whenever possible

If after follow-up, return to baseline status or stabilization cannot be established, an explanation should be recorded in the study record.

10.3 Reporting of SAEs and Unexpected Adverse Reactions

The QI will be responsible for classification of an AE as an SAE within 24 hours of notification. Causality should be signed off by the QI prior to reporting to ethics and regulatory bodies. Notification of any SAEs must be made in writing to the study Sponsor. The IRB will be notified of all product related SAEs and unexpected adverse reactions. All blinded SAE's or unblinded-participant-on-active product SAE's will be reported to the Natural and Non-prescription Health Products Directorate (NNHPD) Clinical Trial Unit in an expedited manner.

KGK Science Inc. must notify the NNHPD of all blinded or unblinded-participant-on-active product SAEs and reactions as follows:

If it is neither fatal or life threatening, within 15 calendar days after the day on which the Sponsor becomes aware of the information; and

If it is fatal or life threatening, must be reported as soon as possible, but not later than seven (7) days after the day on which the Sponsor becomes aware of the information.

11 STATISTICAL EVALUATION

11.1 Determination of Sample Size

Assuming placebo participants would experience 1.43 episodes of URTIs and 7.42 duration days of URTI symptoms during 84 days of follow up (22), a sample size of 100 participants (50 participants per arm) has a power of 80% to detect a rate of \leq 0.76 for the number of episodes of URTIs and \leq 5.80 for the duration days of URTI symptoms in the Bacillus coagulans SNZ 1969 group using Poisson regression model.

In addition, a sample size of 100 participants could detect an effect size ≥ 0.63 in the AUC of GITI symptom scores and in the AUC of the Additional Respiratory Tract Symptoms questionnaire, and a difference of ≥27.8 score.day in the mean of AUC of CARIFS daily total symptom scores between Bacillus coagulans SNZ 1969 and placebo groups assuming standard deviations equal to 52.96 and 32.85 score.day for Bacillus coagulans SNZ 1969 and placebo groups (22), respectively, using two-sample t-test with 80% power, 2-sided 5% significance level, and 20% dropout rate.

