9.7.7 Canadian Acute Respiratory Illness Flu Scale (CARIFS)

The Canadian Acute Respiratory Illness Flu Scales (CARIFS) is an 18-item questionnaire for children that assesses respiratory illness severity across three domains: symptoms, function and parental impact (**Section 16.2**). Each item is answered on a 4-point scale (no problem = 0, minor problem = 1, moderate problem = 2, major problem = 3), with a higher score denoting a more severe illness (20,21). Participants will complete the CARIFS daily throughout run-in and the study period as part of their study diary. As referenced by *Lazou Ahren et al.* (2020) and *Singh et al.* (2024), incidence, duration, and severity of cold and flu will be defined as the following (21,22):

- *Incidence* will be defined as two or more consecutive days with scores above zero (no problem) in at least two symptoms (headache, sore throat, muscle aches or pain, fever, cough, nasal congestion or runny nose, and vomiting; items 10–16) listed on the CARIFS (21).
- *Duration* will be defined as the length of time from an onset of an incidence (defined above) until the last day with symptoms followed by two days with a 0 score
- Severity will be calculated using two methods. 1) The mean total severity score per day of the individual items per incidence of cold or flu symptoms, and 2) area under the curve (AUC) of daily total symptom scores.

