To assess the goodness of fit of the log link models, the Poisson regression model and the negative binomial regression model will be applied to the same dataset and then the Likelihood Ratio Test will be performed. If the p-value of the test is less than 0.05, then we will use the negative binomial model as it offers a better fit of the count data.

To evaluate the adequacy of ANCOVA model, diagnostics including Q-Q plots (for assessing the normality of error terms) and plots of residuals versus fitted values (to examine if the residuals are independent and have constant variance) will be generated. If these diagnostic plots indicate deviations from the model's assumptions, ranks or other transformation of the dependent variable, will be implemented.

Two-sided probabilities ≤ 0.05 will be considered statistically significant. All statistical analysis will be completed using the R Statistical Software Package Version 4.3.2 or newer for Microsoft Windows.

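### The 80% power for URTI duration days (7.42 vs 5.80) holds only if illness days are pure Poisson; if 7.42 is total days per child and episodes are Poisson, it is about 13–26%

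*Protocol*

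**What the plan says.** Protocol 11.1 begins: "Assuming placebo participants would experience 1.43 episodes of URTIs and 7.42 duration days of URTI symptoms during 84 days of follow up". It then says that "a sample size of 100 participants (50 participants per arm) has a power of 80"% to detect an active-arm rate at or below "0.76 for the number of episodes of URTIs" and at or below "5.80 for the duration days of URTI symptoms in the Bacillus coagulans SNZ 1969 group using Poisson regression model". No SD or dispersion is given for either count. The following sentence, on the AUC measures, uses SDs of 52.96 and 32.85 from the cited source and gives a "2-sided 5% significance level, and 20% dropout rate".

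Section 9.7.7 defines an incidence as "two or more consecutive days with scores above zero (no problem) in at least two symptoms". Its rule for duration reads: "length of time from an onset of an incidence (defined above) until the last day with symptoms followed by two days with a 0 score". Section 11.3 analyses incidences and duration days by Poisson or negative binomial regression and chooses between them with a likelihood ratio test: "If the p-value of the test is less than 0.05, then we will use the negative binomial model". Section 5 makes duration part of primary outcome 1.

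**The concern.** A Poisson model for days treats each illness day as an independent event. By the 9.7.7 definition, illness days come in runs of two or more. A child who catches one cold gains several days at once, so total days vary between children by much more than a Poisson count with the same mean. Section 11.1 assumes Poisson variance for episodes and for days in the same sentence. If days are the sum over episodes, both cannot hold.

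Duration is one of three measures on the lead instrument. If its power is far below 80%, a null result would be read as coming from an adequately powered comparison when it was not.

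**Working it through.** **Inputs.** From 11.1: placebo 1.43 episodes and 7.42 days; active 0.76 episodes and 5.80 days; 50 per arm; two-sided 5%; 20% dropout, so 40 evaluable per arm. Alpha and dropout are stated with the t-test and are assumed to apply to the Poisson calculation too. The variance of duration days and the distribution of episode length are not given and must be assumed.

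**Formula.** Wald test on the log rate ratio, with V the variance/mean ratio in each arm:

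power ≈ Φ( |ln(m0/m1)| / SE − 1.96 ), SE = √[ (V0/m0 + V1/m1)/n ].

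Powers below also include the negligible opposite tail.

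**Step 1: reproduce the plan (V = 1, n = 40).**
- Episodes: ln(1.43/0.76) = 0.632; SE = √(1/57.2 + 1/30.4) = 0.224; power 80.4%.
- Days: ln(7.42/5.80) = 0.246; SE = √(1/296.8 + 1/232) = 0.0876; power 80.3%.

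With n = 50 both give 88%. So the plan used pure Poisson variance, children as the unit, and 40 per arm.

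**Step 2: 7.42 as total days per child.** Mean episode length is 7.42/1.43 = 5.19 days. With Poisson episodes of length L, total days have V = E[L²]/E[L], which is at least E[L] = 5.19, reached only if all episodes are equally long. The variance is then 1.43 × 5.19² = 38.5 against a mean of 7.42. With the same V in both arms:

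| Assumed episode length | V | Power, n = 40 | Power, n = 50 |
|---|---|---|---|
| Constant | 5.19 | 23.5% | 28.1% |
| Geometric, 2-day minimum | 7.76 | 17.2% | 20.4% |
| Geometric | 9.38 | 15.1% | 17.7% |
| Exponential | 10.4 | 14.1% | 16.4% |

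For the first row, SE = 0.0876 × √5.19 = 0.200 and 0.246/0.200 = 1.23.

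Letting the arms differ widens the range:
- Active arm with 1.43 constant-length episodes of 5.80/1.43 = 4.06 days: 26.1% (31.3% at n = 50).
- Active arm with 0.76 episodes of 5.80/0.76 = 7.63 days, geometric lengths in both arms: 12.7% (14.7% at n = 50).

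At V = 5.19 in both arms, 80% power would need (1.96 + 0.84)² × 5.19 × (1/7.42 + 1/5.80)/0.246² ≈ 207 evaluable per arm, or 258 randomised per arm.

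**Step 3: the analysis that 11.3 would select.** Data of this kind were simulated with 40 per arm, 600 runs per scenario, and near-constant or 2-day-minimum geometric lengths. The likelihood ratio test chose the negative binomial in every run. That model gave 6–15% power, with type I error of 1.5–3.7%. A Pearson-scaled Poisson model gave 15–27% power. The unscaled Poisson test had type I error of 38–47%.

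**Step 4: 7.42 as days per episode.** Only children with an episode contribute. Expected numbers are 40 × (1 − e^−1.43) = 30.4 and 40 × (1 − e^−0.76) = 21.3. With one value per child and V = 1, SE = √[1/(30.4 × 7.42) + 1/(21.3 × 5.80)] = 0.112; 0.246/0.112 = 2.20; power about 60%. Counting every expected episode as a unit (57.2 and 30.4) gives SE = 0.0896 and about 79%.

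**Step 5: episodes.** With negative binomial dispersion k, SE² = (1/1.43 + 1/0.76 + 2k)/40. Power is about 71% at k = 0.25 and 63% at k = 0.5. Both values of k are assumptions.

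**The case against.** The arithmetic is right for the model that 11.1 names; the dispute is over a variance assumption. A reader might infer that the protocol's figures by themselves rule out Poisson variance, or that true power is 14–23%. The documents support neither.

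- **Meaning of 7.42.** Section 9.7.7 defines duration per incidence. Section 5 lists total days of illness as a separate secondary outcome, and 11.3 lists duration days and illness days separately. On the per-episode reading the compound-sum variance does not apply. This objection stands, but it does not rescue the 80%: that figure reproduces with 40 children per arm, whereas one value per affected child gives about 60%. The 79% needs episodes as independent units with Poisson variance, which 11.1 does not describe.
- **The floor of 5.2.** It needs Poisson episode counts as well as the two means. With constant length, if every child had one or two episodes, V would be 0.43 × 0.57 × 5.19²/7.42 = 0.89. A binomial with at most three episodes gives about 2.7. But 11.1 itself assumes Poisson episodes.
- **Episode lengths.** The choices behind any range are assumptions, so only a conditional range is justified.
- **The model switch.** Section 11.3 treats overdispersion as a contingency, not an expectation. The switch guards against false positives, and the confidence intervals for rate ratios would show imprecision. Neither restores power.

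**Conclusion.** The 80% power claim for 5.80 versus 7.42 days is not supported. If 7.42 is total days per child and episodes are Poisson with mean 1.43, power is about 13–26% with 40 evaluable per arm and at most about 31% with 50. In simulation it was 6–15% with the negative binomial model. If 7.42 is days per episode, the calculation uses the wrong unit, and power with one value per affected child is about 60% even with Poisson variance. The exact figure cannot be fixed without the SD of duration days, which the protocol does not give. The 80% for episodes is correct only without overdispersion. The defect lies in the stated power, not in the planned analysis.

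**What to change.** Keep N = 100 and rewrite the first paragraph of 11.1:

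1. State whether 7.42 is total days per child over 84 days or days per episode, and make 9.7.7 and 11.3 agree.
2. Withdraw the 80% power claim for 5.80 days.
3. Recompute power and the detectable mean under an overdispersed model (negative binomial or scaled Poisson), using the SD or dispersion of duration days from the cited source, as was done for AUC.
4. If that SD is unavailable, give power as a conditional range with its assumptions. Do not substitute a mean of about 4.0 days as an 80%-power figure: 4.0 comes only from the scaled-Poisson formula with constant episode length, and a negative binomial simulation of that case (400 runs, 40 per arm) gave 62% power.
5. Say that the 80% for 1.43 versus 0.76 episodes assumes no overdispersion, with an illustration such as about 71% and 63% at assumed dispersions of 0.25 and 0.5.

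The cost is a wording change in 11.1, with any matching edits to 9.7.7 and 11.3, and less favourable stated figures. No extra participants are needed.
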